Appendix 1. Draft Qualitative Interview Guides

The investigators will lead a semi-structured cognitive interview with each patient participant in the Open Trial of the Development Phase to gather information that will provide guidance in developing the Text-Based Adherence Game intervention. Following the Introduction outline below is an outline for the Verbal Interview. Each interview topic is followed by broad and generally open-ended questions. Interviewers will be instructed to ask more specific follow-up questions to probe responses to the initial open-ended questions.

Introductions

Overview: The intent of this portion of the agenda is to welcome the participant and make them as comfortable as possible by explaining the interview process and letting them know what to expect from the experience. Additionally, the investigator will explain rules concerning confidentiality, and the use of data.

- Introduce Investigator
- Explain that the overall purpose of interview is to elicit discussion about the participant's experiences with participating in the Text-Based Adherence Game.
- Sample dialogue: *"Thank you so much for agreeing to be a part of this interview today.*
We are here today to learn about your experience with playing the Text-Based Adherence Game (referred to as TAG). As you know, our idea is to create a game that is played through text messages. The game should be fun and help young people connect with social support and focus on their HIV treatment. We want to know what people think about the game and if you have any suggestions for its improvement. You are the expert in this area. We really need to learn from you in order to make this program successful.
- Ground rules: *"You do not have to answer any questions you are uncomfortable with.*
There is no right or wrong answers. We're interested in all opinions."
- Confidentiality: *"We work hard to make sure everything said in the interview will not be shared with anyone outside of the research team unless you tell us about a situation where you or someone else is in danger."*
- Digital Recording: *"Recordings are not shared with anyone outside of the research team, they are kept safe and private. When information is taken from the recording, participants will be identified by a number only and names will not be used. Tapes will be erased once transcribed and summarized."*

Verbal Interview

Feedback on the Game: The participants will be asked to talk about their impressions of the Text-Based Adherence Game (TAG).

- “Tell me about your experience playing TAG.”
- “What aspects of TAG did you like the most?”
- “How was the game helpful to your HIV treatment?”
- “In what ways did the game influence how you take ART?”
- “In what ways did the game influence your feelings towards ART?”
- “In what ways did the game influence your ability to attend appointments?”
- “What did you learn from the game?”
- “What aspects of TAG would you want to change?”
- “Tell me your thoughts about the theme of the game.”
- “What did you think of the frequency of text messages?”
- “How difficult was it to read and understand the text messages?”
- “What did you think about competing against other young people?”
- “What did you think about having a treatment buddy involved?”
- “Tell me about getting asked to receive a phone call from the clinic?”
- “What would other young people living with HIV like about this game?”
- “Did you ever worry about privacy when playing TAG?”
- “If all young people at the clinic started playing this game tomorrow, what’s the first thing you’d do to improve it?”

Closing

Overview: the participants will be thanked for their time and efforts

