on Centers for Disease Control and Prevention guidelines (44) led by a bachelors-level clinic counselor, as needed contact with counselors, and access to a clinic social event held once per year. They will then be shown the game by a trained RA. The basic elements of the game will be demonstrated and YPLH will have an opportunity to interact with the system, with study staff, to build interest and understanding. Participants will be asked permission to enroll a treatment buddy to participate in the game as well. This person will be consented by study staff. The game also pairs participants with a peer educator who has shown good medical adherence by clinic report and is trained to provide phone peer support. Three iterations of increasing game length (two, four, and eight weeks) and number of participants ($n = 6, 8$, and 10) will test game prototypes. After each iteration participants will be assessed with a semi-structured cognitive interview (45) to gauge participants' opinions of the game, and its clinical utility, relevance, strengths and weaknesses, ease of use, and ability to capture their experiences (See Appendix 1 for interview guide). Audio from cognitive interviews will be digitally recorded and transcribed. They will also complete quantitative measures for similar feedback. In addition, participants will be assessed before and after the third iteration on main study variables to explore shifts in our primary and secondary outcomes. Information gained after each iteration will be used by research staff to alter the game. Study staff will also contact participants after they enroll via a phone call to trouble shoot problems playing the game. YPLH will be remunerated with an allowance of 40 Cedis for each assessment. They will also be given 40 Cedis worth of prepaid phone credits to send text messages. Treatment monitors will be compensated 40 Cedis.

[figure not shown]

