Hypothesis One (Aim 1). The Text-Based Adherence Game will be feasible, appealing, and useful. YPLH in the third open trial iteration of the Text-Based Adherence Game will show shifts in primary and secondary outcomes in the expected directions from pre-post assessments.

Hypothesis Two (Aim 2). Compared to participants in the control group, participants in the Text-Based Adherence Game will show at 6 and 12 months post-intervention: improved ART adherence, clinic attendance, biologic functioning (lower

Figure 5. Assessment Schedule

HIV viral load, higher CD4 count), and shifts in secondary outcomes (social support, self-efficacy, etc.) consistent with adherence promotion. Repeated measures ANCOVAs will be used to test differences over time between study conditions on each outcome variable. Missing data will be handled using multiple imputation. Potential imbalance between treatment conditions on baseline characteristics will be addressed using inverse probability of treatment weights (51). Power: As this is a pilot study and the impact of the intervention is not known, there may not be adequate power to determine its efficacy; also, pilot studies are not designed to provide accurate estimates of effect sizes upon which to base large trials(52). However, the small pilot may provide a “signal” of impact on its primary outcomes and we will examine the effects of the intervention on secondary outcomes based on Social Action Theory. We assume that retention over one year is at least 86% based on past studies conducted in Ghana (31, 53) thus 52 cases of the 60 enrolled in the pilot are available for analysis. Power analyses were run with G*Power 3(54). The model assumed 3 assessments with 52 individuals. The analyses with alpha of 0.05 and power 0.80 will be able to detect small to medium effects.

DISSEMINATION OF RESULTS

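### In the draft open-trial interview guide, all four questions on the game's effect on treatment assume an effect, and one assumes a benefit, so these answers are at risk of leading-question bias

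*Combined protocol and SAP*

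**What the plan says.** The section on the iterative open trial (Procedures) has every participant interviewed after each iteration. The stated purposes include clinical utility and both strengths and weaknesses. The same section adds: "Information gained after each iteration will be used by research staff to alter the game". Hypothesis One in the Data Analytic Plan states: "The Text-Based Adherence Game will be feasible, appealing, and useful".

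Appendix 1 gives the draft guide, in interviews led by the investigators. The sample introduction tells the participant: "The game should be fun and help young people connect with social support and focus on their HIV treatment". The list headed Feedback on the Game then contains four questions on effect on treatment. The first concerns treatment as a whole: "How was the game helpful to your HIV treatment". The second turns to medication-taking and is put this way: "In what ways did the game influence how you take ART". The third and fourth repeat that same form of words for two further subjects, namely how the participant feels about ART and whether visits to the clinic are kept.

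A fifth, related question follows directly: "What did you learn from the game".

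**The concern.** A question that takes an effect for granted makes it harder to report none. The participant must first reject the premise, in front of a member of the team that developed the game. According to the Executive Summary, two of the three investigators are also doctors at the clinic where the participant receives care. A null answer is exactly what an assessment of clinical utility needs to be able to pick up.

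Two uses are at stake: the evidence for the word useful in Hypothesis One, and the feedback used to change the game between iterations. A game that left adherence or attendance unchanged could look more useful in the interviews than participants found it.

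**Working it through.** There is no figure in the plan to reproduce. The check is a reading and count of the prompts under Feedback on the Game, numbered here in the order in which they appear.

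**All prompts.**

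| Type | Prompts | Count |
|---|---|---|
| Neutral opener | 1 | 1 |
| Liking (most liked; what other young people would like) | 2, 15 | 2 |
| Effect on treatment | 3, 4, 5, 6 | 4 |
| Learning | 7 | 1 |
| Inviting criticism (change, reading difficulty, privacy, first improvement) | 8, 11, 16, 17 | 4 |
| Neutral on a feature (theme, frequency, competition, treatment buddy, clinic call) | 9, 10, 12, 13, 14 | 5 |

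Sum: 1 + 2 + 4 + 1 + 4 + 5 = 17.

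**The effect prompts.**

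| Prompt | Subject | Assumes an effect | Assumes benefit | Wording offers no effect |
|---|---|---|---|---|
| 3 | HIV treatment | yes | yes | no |
| 4 | taking ART | yes | no | no |
| 5 | feelings towards ART | yes | no | no |
| 6 | attending appointments | yes | no | no |

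So 4 of 4 assume an effect (5 of 5 if the learning question is counted, although it is not strictly about treatment). One of 4 assumes benefit, 3 of 4 leave the direction open, and 0 of 4 offer no effect as an answer.

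**Order.** The effect prompts are numbers 3 to 6. The first prompt that invites criticism is number 8. The statement of what the game should do comes earlier still, in the introduction.

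**Do other instruments ask the same thing in a balanced way?**

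- Client Satisfaction Questionnaire, item 6, allows both no help and a worsening, but about issues important to the participant, not about HIV treatment.
- The Session Evaluation Form asks for the least useful aspect, and its first item lets a participant disagree that much was learned.
- None of the items on either form asks about taking ART or attending appointments.
- The main outcome measures are taken before and after the third iteration only. The section Participant Involvement puts this at 10 of the 24 participants, so 24 - 10 = 14 have no pre-post measurement.

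On the text available, the interview is the only place where those 14 are asked directly how the game affected ART-taking or attendance. This reading assumes that the figures not shown, including the assessment schedule, add no further measure.

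**Comparison within the document.** The cognitive interview guide for parents and adolescents asks both what they like and what they do not like about the idea. The Session Evaluation Form pairs the most with the least useful aspect. Appendix 1 asks only what was liked most.

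**The case against.** A reader might infer that the open-trial feedback as a whole is biased towards finding the game useful. The documents do not support that:

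- Three of the four effect questions presuppose influence, not benefit. A participant can answer directly that the game made attendance harder.
- The guide opens with a neutral prompt. Its introduction asks for suggestions and says that no answer is wrong and that every opinion is welcome. Interviewers are told to probe, though the content of the probes is not given.
- By the time of the interview participants have been shown the game and have played it, so its purpose is not news to them.
- The two satisfaction forms accept null and negative answers.

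A reader might also infer that harms such as irritating messages or shaming competition would stay hidden. They need not: message frequency and competition each have a neutral prompt. Nor do the documents say that the interviews alone decide what is altered. The sentence on altering the game refers to information gained after each iteration, and the quantitative measures are among the things collected.

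All of this stands, and it narrows the point. It does not remove it. No effect question offers no effect as an answer, one assumes help, and the balanced instruments do not ask about ART-taking or attendance.

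**Conclusion.** The point holds as a risk of bias confined to the answers on perceived treatment effect. All four such questions are leading as to whether there was an effect, and one is leading towards benefit. Neither the size nor the realised direction of any bias can be derived from the documents. The partial offsets are real but do not cover ART-taking or attendance for the 14 participants without pre-post measures.

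The interviews belong to the development phase and do not enter the randomised comparison, which is not directly affected. This is a minor point, worth making because the remedy is essentially free.

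**What to change.** Reword the draft guide in Appendix 1:

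- Helpfulness: *How, if at all, did the game affect your HIV treatment, for better or worse?*
- Use the same form for taking ART, feelings towards ART and attending appointments.
- Learning: *What, if anything, did you learn?*
- Follow the prompt on what was liked most with one on what was liked least.

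Moving the introduction's sentence on what the game should do to the end would also help, but is secondary.

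The cost is an edit to a document still marked as a draft: no added staff, and one short extra prompt. If the interviews have already been held, report the wording used and do not rely on these answers alone as evidence of usefulness. Read them beside the satisfaction forms and, for the third iteration, the pre-post measures.

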Appendix 2: Chart Review Data Abstraction Form

1) Today's date:
(MM)_____(DD)_____(YY)_____

2) Date of first presentation to KBTH:
(MM)_____(DD)_____(YY)_____

3) Age (years) _____

4) Gender
 1 – Male
 2 – Female

5) Marital Status
 1 – Single
 2 – Married
 3 – Divorced
 4 – Separated
 5 – Cohabiting
 6 – Not Available

6) Highest education level attained
 1 – None
 2 – Primary
 3 – JSS
 4 – MSLC
 5 – Sec/Tech
 6 – University

7) Employment/occupation at presentation

8) Employment status at presentation
 1 – Full time
 2 – Part time
 3 – On leave
 4 – Unemployed
 5 – Unknown

9) Dependent children (aged <18 years)
 1 – Total number

 2 – How many are HIV+

10) Funding type
 1 – Patient out-of-pocket
 2 – Medical insurance
 3 – Special project
 4 – Employer sponsored
 5 – Unknown
 6 – Other: _____

11) HIV status at presentation:
 Known positive
 Diagnosed at admission

12) Current WHO stage
 1 – Stage I
 2 – Stage II
 3 – Stage III
 4 – Stage IV

13) Current Drug Therapy (check all that apply):
 1 – Stavudine
 2 – Zidovudine
 3 – Lamivudine
 4 – Abacavir
 5 – Tenofovir
 6 – Didanosine
 7 – Nevirapine
 8 – Efavirenz
 9 – Combivir (zidovudine and lamivudine)
 10 – Kaletra (lopinavir/r)
 11 – Nelfinavir
 13 – Other:

14) Most recent CD4 cell count: _____

15) Date of most recent CD4 cell count test:

16) Most recent viral load: _____

17) Date of most recent viral load test:

18) Detectable viral load in past six months:
 – Yes
 – No

19) Date of ART initiation:
(MM)_____(DD)_____(YY)_____

20) Number of clinic appointments missed in the past 6 months

21) Number of clinic appointments kept in the past 6 months

22) Number of clinic appointments missed in the past 12 months

23) Number of clinic appointments kept in the past 12 months

24) Longest period without an appointment (months):

25) Route of HIV infection
 1 – Perinatal
 2 – Behavioral
 3 – Unknown

Appendix 3: Questionnaire and Satisfaction Surveys

ALL QUESTIONNAIRE ITEMS WILL BE READ TO PARTICIPANTS AND ADMINISTERED BY A COMPUTER PROGRAM WITH RESEARCH STAFF PRESENT FOR ASSISTANCE.

Demographic Survey

Age	
Gender	1- Male 2- Female 3- Other
Ethnicity	1- Akan 2- Ga/Dangbe 3- Ewe 4- Northern Tribes 5- Multiple 6- Other
What language do you speak at home?	1- Twi/Fante/Bono 2- Ga/Dangbe 3- Hausa 4- Ewe 5- English 6- Other
Location of home	1- Kumasi 2- Outside of Kumasi
Distance traveled to Fevers Unit	1- 5km or less 2- 6-10km 3- 11-15km 4- 16-20km 5- 21-25km 6- 26-30km 7- 31-35km 8- 36-40km 9- 41km or more
Time to travel to Chest Clinic	1- less than 30 minutes 2- 30 minutes to 1 hour 3- 1-2 hours 4- more than 2 hours
How do you get to Chest clinic?	1- Public transportation 2- Walk 3- Private car 4- Other
How much does it cost you (GHS) to get to Chest clinic?	
Highest Education Completed	1- None 2- Primary 3- Secondary 4- Higher education

Currently in school	1- Yes, secondary (boarding school) 2- Yes, secondary (not boarding school) 3- Yes, higher education 4- No
Live with parents or caregivers	1- Yes 2- No
Parents died as a result of AIDS	1 - Yes, one parent 2 - Yes, two parents 3 - No
Does anyone else you live with have HIV?	1- Yes 2- No
Sexual orientation	1- Straight (heterosexual) 2- Gay or lesbian (homosexual) 3- Bisexual 4- Other
Marital status	1- Single/never married 2- Married 3- Divorced/separated 4- Widowed
Relationship status	1- In a relationship, living with partner 2- In a relationship, not living with partner 3- Not in a relationship
HIV status of partner	1- HIV positive 2- HIV negative 3- Not sure
Do you have children?	1- Yes 2- No
If yes, how many?	
Religion	1- No religion 2- Catholic/Anglican 3- Protestant 4- Other Christian 5- Muslim 6- Traditionalist/spiritualist 7- Other
Employment	1- Unemployed 2- Self-employed 3- Private or government employment
Monthly household income (GHS)	1- No income 2- 1-99 GHS per month 3- 100-199 GHS per month 4- 200-299 GHS per month 5- 300-399 GHS per month 6- 400-499 GHS per month 7- 500 GHS or more per month

How many people are in your household?	_____
Which of the following best describes the main dwelling where you live?	1. Formal dwelling (such as a house) 2. Informal dwelling (such as shack or tent)

Subjective Social Standing

Instructions – First Ladder

Think of this ladder as showing where people stand in their communities. People define community in different ways. Please define it in whatever way is most meaningful to you. At the top of the ladder are the people who have the highest standing in their community. At the bottom are the people who have the lowest standing in their community. Where would you place yourself on this ladder? Place an X on the rung where you think you stand at this time of your life relative to other people in your community.

Instructions – Second Ladder

Think of this ladder as showing where people stand in Ghana. At the top of the ladder are the people who are the best off – those who have the most money, the best education, and the most respected jobs. At the bottom are the people who are the worst off – who have the least money, least education, and the least respected job or no job. The higher up you are on this ladder, the closer you are to the people at the top.; the lower you are, the closer you are to the people at the bottom. Where would you place yourself on this ladder? Place an X on the rung where you think you stand at this time of your life relative to other people in the Ghana.

Food Security Questions

1. “We worried whether our food would run out before we could get more.”
Was that often true, sometimes true, or never true for your household in the last month?
2. “The food that we had just didn’t last, and we couldn’t get more.”
Was that often, sometimes, or never true for your household in the last month?
3. “We couldn’t get the kinds of foods that give us good health.”
Was that often, sometimes, or never true for your household in the last month?
4. In the last month, did (you/you or other adults in your household) ever reduce the amount of food you ate or skip meals because there wasn’t enough food? Yes or No
5. In the last month, did you ever eat less because there wasn’t enough food? Yes or No.
6. In the last month, were you ever hungry but didn’t eat because there wasn’t enough food? Y/N
7. In the last month, did you lose weight because you didn’t have enough food to eat? Yes or No.
8. In the last month, did you or other adults in your household ever not eat for a whole day because there wasn’t enough food? Yes or No.

Self-Efficacy for Adherence to HIV Care

In the past 6 months, how many doctor’s appointments have you missed?

| ____ | ____ | “Appointments”

Please answer the following questions using these response options:

1 “Very Sure I Can”
2 “Pretty Sure I Can”

3 “Not Sure if I Can or Cannot”
4 “Pretty Sure I Cannot”

5 "Very Sure I Cannot"

How sure are you that you can keep doctor and other health care appointments? _____
 How sure are you that you can do better with keeping doctor and other health care appointments?"_____

How sure are you that you can keep doctor and other health care appointments even if you were very tempted not to?"_____

"How sure are you that you can take the right amounts of your medicine at the right times?"

"How sure are you that you can do better with taking the right amounts of your medicine at the right times?"_____

"How sure are you that you can take the right amounts of your medicine at the right times even if you were very tempted not to?"_____

ART Perceived Norms

1. Based on what you personally believe, not just what your doctor tells you, what is a good rate of adherence? _____ (0 to 100%)
2. How many missed doses would be of concern for you out of your next 10 doses? _____
3. Based on what you personally believe, not just what your doctors tells you, what is the rate of adherence for most people your age? _____ (0 to 100%)

Problem-Solving Inventory**Instructions**

How much do you agree or disagree with the following statements?

Strongly Agree

1

2

3

4

5

6

Strongly Disagree

1. I am usually able to think up creative and effective alternatives to solve a problem. _____
2. I have the ability to solve most problems even though initially no solution is immediately apparent ____
3. Many problems I face are too complex for me to solve. ____
4. I make decisions and am happy with them later. ____
5. When I make plans to solve a problem, I am almost certain that I can make them work. ____
6. Given enough time and effort, I believe I can solve most problems that confront me. ____
7. When faced with a novel situation I have confidence that I can handle problems that may arise. _____
8. I trust my ability to solve new and difficult problems ____
9. After making a decision, the outcome I expected usually matches the actual outcome. ____
10. When confronted with a problem, I am unsure of whether I can handle the situation. ____
11. When I become aware of a problem, one of the first things I do is to try to find out exactly what the problem is ____
12. When a solution to a problem was unsuccessful, I do not examine why it didn't work. ____
13. When I am confronted with a complex problem, I do not bother to develop a strategy to collect information so I can define exactly what the problem is. ____
14. After I have solved a problem, I do not analyze what went right or what went wrong ____
15. After I have tried to solve a problem with a certain course of action, I take time and compare the actual outcome to what I thought should have happened. ____
16. When I have a problem, I think up as many possible ways to handle it as I can until I can't come up with any more ideas ____
17. When confronted with a problem, I consistently examine my feelings to find out what is going on in a problem situation. ____

18. When confronted with a problem, I tend to do the first thing that I can think of to solve it. ____

19. When deciding on an idea or possible solution to a problem, I do not take time to consider the chances of each alternative being successful. ____

20. When confronted with a problem, I stop and think about it before deciding on a next step. ____

21. I generally go with the first good idea that comes to my mind. ____

22. When making a decision, I weigh the consequences of each alternative and compare them against each other. ____

23. I try to predict the overall result of carrying out a particular course of action, ____

24. When I try to think up possible solutions to a problem, I do not come up with very many alternatives. ____

25. I have a systematic method for comparing alternatives and making decisions. ____

26. When confronted with a problem, I do not usually examine what sort of external things my environment may be contributing to my problem. ____

27. When I am confused by a problem, one of the first things I do is survey the situation and consider all the relevant pieces of information. ____

28. When my first efforts to solve a problem fail, I become uneasy about my ability to handle the situation. ____

29. Sometimes I do not stop and take time to deal with my problems, but just kind of muddle ahead. ____

30. Even though I work on a problem, sometimes I feel like I am groping or wandering, and am not getting down to the real issue. ____

31. I make snap judgments and later regret them. ____

32. Sometimes I get so charged up emotionally that I am unable to consider many ways of dealing with my problems. ____

ART Outcome Expectancies

Instructions

We're going to ask you to think about different situations having to do with how people take their HIV medications. Use the following response options to answer the questions.

1 Not at all likely
2 Somewhat likely

3 Moderately likely
4 Very likely

Q1. If you did not take your HIV medications as they are prescribed to you, how likely is it that you would experience worsening health? ____

Q2. If you did not take your HIV medications as they are prescribed to you, how likely is it that your immune system would get weaker? ____

Q3. If you did not take your HIV medications as they are prescribed to you, how likely is it that the virus would get stronger? ____

Q4. If you did not take your HIV medications as they are prescribed to you, how likely is it that you would feel better than you do now? ____

Q5. If you did not take your HIV medications as they are prescribed to you, how likely is it that your life would be easier? ____

Q6. If you did not take your HIV medications as they are prescribed to you, how likely is it that it will not make a difference? ____

Q7. If you did not take your HIV medications as they are prescribed to you, how likely is it that your life would be shorter? ____

Motivational Readiness to Adhere to HIV Medications

Instructions

"How ready are you to take HIV medication as prescribed."

Not Ready	Unsure	Completely Ready
1 2 3 4 5 6 7 8 9 10		

“How ready are you to get to HIV medical appointments (at least 4 times a year).”

1 2 3 4 5 6 7 8 9 10

MOS Social Support Survey

Instructions

INSTRUCTIONS: People sometimes look to others for companionship, assistance, or other types of support. How often is each of the following kinds of support available to you if you need it? Circle one number on each line.

	None of the time	A little of the time	Some of the time	Most of the time	All of the time
Emotional/Informational Support					
Someone you can count on to listen to you when you need to talk	1	2	3	4	5
Someone to give you information to help you understand the situation	1	2	3	4	5
Someone to give you good advice about a crisis	1	2	3	4	5
Someone to confide in or talk to about yourself or your problems	1	2	3	4	5
Someone whose advice you really want	1	2	3	4	5
Someone to share your most private worries and fears with	1	2	3	4	5
Someone to turn to for suggestions about how to deal with a personal problem	1	2	3	4	5
Someone who understands your problems	1	2	3	4	5
Tangible support					
Someone to help you if you were confined to bed	1	2	3	4	5
Someone to take you to the doctor if you needed it	1	2	3	4	5
Someone to prepare your meals if you were unable to do it yourself	1	2	3	4	5
Someone to help with daily chores if you were sick	1	2	3	4	5
Affectionate support					
Someone who shows you love and affection	1	2	3	4	5
Someone to love and make you feel wanted	1	2	3	4	5
Someone who hugs you	1	2	3	4	5

	of the time	of the time	of the time	the time	the time
Positive social interaction					
Someone to have a good time with	1	2	3	4	5
Someone to get together with for relaxation	1	2	3	4	5
Someone to do something enjoyable with	1	2	3	4	5
Additional item					
Someone to do things with to help you get your mind off things	1	2	3	4	5

HIV Care Provider Social Support

Instructions

“Care providers have different styles in dealing with patients. We would like to know more about how you feel about your care provider. Answer these questions by thinking of the main health care provider you see at your HIV clinic. Please indicate how you felt during your most recent visit to your care provider. Your responses are confidential. Please be honest and truthful. Indicate how much you agree with each of the following statements.”

1 “Strongly disagree”

4 “Somewhat agree”

2 “Somewhat disagree”

5 “Strongly agree”

3 “Neutral”

1. “I feel that my care provider has provided me with choices and options.”
2. “I feel understood by my care provider.” _____
3. “My care provider conveys confidence in my ability to make changes.” _____
4. “My care provider encourages me to ask questions.” _____
5. “My care provider tries to understand how I see things before suggesting a new way to do things.” _____

Adherence and Risk Reduction Social Support

Instructions

These questions are about other people in your life. Please tell me how much you agree or disagree with each sentence.

1 Strongly disagree

4 Agree

2 Disagree

5 Strongly agree

3 Uncertain

1. “There are people in my life that are supportive about keeping medical appointments” _____
2. “There are people in my life that are supportive about taking HIV medication” _____
3. “There are people in my life that are supportive about using condoms” _____
4. “There are people in my life that are supportive about telling your partner about your HIV status” _____
5. “There are people in my life that are supportive about avoiding drug use” _____
6. “There are people in my life that are supportive about avoiding alcohol use” _____

Modified Social Provisions Scale

Instructions

The next set of questions are about a particular person who you rely on the most for helping you with your HIV treatment on a daily basis. This person is typically a friend, parent or other family member, or your treatment supporter (also known as a treatment buddy) but they can also be a peer educator, clinic counselor, or someone else. He or she may remind you to take your medication, make sure you get to your HIV clinic appointments, or help you in other ways. Please identify this person:

- 1- Treatment supporter (treatment buddy)
- 2- Same-age or younger friend
- 3- Older adult friend
- 4- Parent
- 5- Other family member (Please describe your relationship to this person: _____)
- 6- Peer educator
- 7- Clinic counselor
- 8- Someone else (Please describe your relationship to this person: _____)

I'm going to ask you about your relationship with this person. Please tell me how much each statement describes your situation by using these responses. So, for example, if you feel a statement is VERY TRUE you would say Strongly Agree. If you feel a statement CLEARLY does not describe your relationship, you would answer Strongly Disagree?"

Strongly Disagree = 1

Agree = 3

Disagree = 2

Strongly Agree = 4

1. This person will help me if I really need it.
2. I do not have a close relationships with my this person.
3. I can't turn to this person in times of stress.
4. This person calls on me to help him/her.
5. This person likes the same social activities I do.
6. This person does not think I am good at what I do.
7. I feel responsible for taking care of this person.
8. This person thinks the same way I do about things.
9. I do not think that this person respects what I do.
10. If something went wrong, this person would help me.
11. I have a close relationship with this person that make me feel good.
12. I can talk to this person about decisions in my life.
13. This person values my skills and abilities.
14. This person does not have the same interests and concerns as me.
15. This person does not need me to help take care of them.
16. This person is a trustworthy person I can turn to if I have problems.
17. I feel a strong emotional tie with this person.
18. I cannot count on this person for help if I really need it.
19. I do not feel comfortable talking about problems with this person.
20. This person admires my talents and abilities.
21. I do not have a feeling of closeness with my this person.
22. This person does not like to do the things I do.
23. I can count on this person in an emergency.
24. This person does not need me to take care of him/her.

Information-Motivation-Behavioral Skills ART Adherence Questionnaire

Instructions and Items

"How much do you agree with each statement?"

- 1. I strongly disagree
- 2. I somewhat disagree
- 3. I neither agree nor disagree

- 4. I somewhat agree
- 5. I strong agree

I1. I know how each of my current HIV medications is supposed to be taken (for example whether or not my current medications can be taken with food, herbal supplements, or other prescription medications). _____

I2. I know what to do if I miss a dose of any of my HIV medications (for example, whether or not to take the pill(s) later). _____

I3. Skipping a few of my HIV medications from time to time would not really hurt my health. _____

I4. I know what the possible side effects of each of my HIV medications are. _____

I5. As long as I am feeling healthy, missing my HIV medications from time to time is OK. _____

I6. I understand how each of my HIV medications works in my body to fight HIV. _____

I7. If I don't take my HIV medications as prescribed, these kinds of medications may not work for me in the future. _____

I8. I believe that if I take my HIV medications as prescribed, I will live longer. _____

I9. I know how my HIV medications interact with alcohol and street drugs. _____

M1. I am worried that other people might realize that I am HIV+ if they see me taking my HIV medications. _____

M2. I get frustrated taking my HIV medications because I have to plan my life around them. _____

M3. I don't like taking my HIV medications because they remind me that I am HIV+. _____

M4. I feel that my healthcare provider takes my needs into account when making recommendations about which HIV medications to take. _____

M5. Most people who are important to me who know I'm HIV positive support me in taking my HIV medications. _____

M6. My healthcare provider doesn't give me enough support when it comes to taking my medications as prescribed. _____

M7. It frustrates me to think that I will have to take these HIV medications every day for the rest of my life. _____

M8. I am worried that the HIV medications I have been prescribed will hurt my health. _____

M9. It upsets me that the HIV medications I have been prescribed can affect the way I look. _____

M10. It upsets me that the HIV medications I have been prescribed can cause side effects. _____

B1. There are times when it is hard for me to take my HIV medications when I drink alcohol or use street drugs. _____

“How hard or easy would it be to do the following?”

- 1. Very hard
- 2. Hard
- 3. Sometimes hard, sometimes easy

- 4. Easy
- 5. Very easy

B2. How hard or easy is it for you to stay informed about HIV treatment? _____

B3. How hard or easy is it for you to get the support you need from others for taking your HIV medications (for example, from friends, family, doctor, or pharmacist)? _____

B4. How hard or easy is it for you to get your HIV medication refills on time? _____

B5. How hard or easy is it for you to take your HIV medications when you are wrapped up in what you are doing? _____

B6. How hard or easy is it for you to manage the side effects of your HIV medications? _____

B7. How hard or easy is it for you to remember to take your HIV medications? _____

B8. How hard or easy is it for you to take your HIV medications because the pills are hard to swallow, taste bad, or make you sick to your stomach? _____

B9. How hard or easy is it for you to make your HIV medications part of your daily life? _____

B10. How hard or easy is it for you to take your HIV medications when your usual routine changes (for example, when you travel or when you go out with your friends)? _____

B11. How hard or easy is it for you to take your HIV medications when you do not feel good emotionally (for example, when you are depressed, sad, angry, or stressed out)? _____

B12. How hard or easy is it for you to take your HIV medications when you feel good physically and don't have any symptoms of your HIV disease? _____

B13. How hard or easy is it for you to take your HIV medications when you do NOT feel good physically? _____

B14. How hard or easy is it for you to talk to your health care provider about your HIV medications? _____

HIV Treatment Readiness Measure (HTRM)

Instructions

“Please rate on a scale of 1 (strongly disagree) to 5 (strongly agree) how true each of the statements below are for you. By HIV health care provider, we mean your doctor, nurse practitioner or physician assistant.”

Use the following response options:

“1=Strongly Disagree”

“4=Agree”

“2=Disagree”

“5=Strongly Agree”

“3=Neither Agree nor Disagree”

